8	DOCUMENT REVISION HISTORY	49

9	REFERENCES	49
10	APPENDICES	50
10.1	Appendix 1: Signature	50
10.2	Appendix 2: Search Strategy for Adverse Events of Interest	51

I. LIST OF ABBREVIATIONS AND KEY TERMS

List of Abbreviations

Abbreviations	Description of abbreviations
AE	Adverse Event
AESI	Adverse events of special safety interest
ALP	Alkaline Phosphatase
ALT	Alanine Transaminase
AML	Acute Myeloid Leukemia
API	Astellas Pharma Inc.
AST	Aspartate Transaminase
ATC	Anatomical Therapeutic Chemical Classification
AUC	Area under the plasma concentration-time curve
AUC ₂₄	Area under plasma concentration-time curve from time 0 to 24
AUC _{inf}	AUC from the time of dosing extrapolated to time infinity
AUC _{last}	AUC from the Time of Dosing to the Last Measurable Concentration
AXL	AXL receptor tyrosine kinase
BLQ	Below the Limit of Quantification
BMI	Body Mass Index
BSA	Body Surface Area
CI	Confidence Interval
CID	Cumulative Incidence of Death
CIR	Cumulative Incidence of Relapse
CL/F	Oral clearance
C _{max}	Maximum concentration
CR	Complete Remission
CR1	1 st Complete Remission
CRc	Composite Complete Remission
CRF	Case Report Form
CRh	Complete Remission with Partial Hematological Recovery
CRi	Complete Remission with Incomplete Hematological Recovery
CRM	Continual Reassessment Method
CRp	Complete Remission with Incomplete Platelet Recovery
CSR	Clinical Study Report
CTCAE	Common Terminology Criteria for Adverse Events
DBP	Diastolic Blood Pressure
DDAS	Dose-Determining Analysis Set
DLT	Dose-Limiting Toxicity
ECG	Electrocardiogram
ECHO	Echocardiogram
ECOG	Eastern Cooperative Oncology Group
eCRF	electronic Case Report Form
EFS	Event Free Survival

Abbreviations	Description of abbreviations
ELN	European LeukemiaNet
ESS	Effective Sample Size
FAB	French-American-British
FAS	Full Analysis Set
FLT3	FMS-like tyrosine kinase-3
FLT3-ITD	FLT3- Internal Tandem Duplication
FLT3-TKD	FLT3- Tyrosine Kinase Domain
GM	Geometric Mean
HLT	High Level Term
HSCT	Hematopoietic Stem Cell Transplantation
ICF	Informed Consent Form
ICH	International Conference on Harmonization
Lambda z	Terminal elimination rate constant
LLOQ	Lower Limit of Quantification
LVEF	Left Ventricular Ejection Fraction
MAS	MRD Analysis Set
MedDRA	Medical Dictionary for Regulatory Activities
MR	Molecular Response
MRD	Minimal Residual Disease
MTD	Maximum Tolerated Dose
MUGA	Multiple Gate Acquisition
NCI	National Cancer Institute
NE	Not Evaluable
NR	No Response
NYHA	New York Heart Association
OS	Overall Survival
PD	Pharmacodynamic
PDAS	Pharmacodynamic Analysis Set
PK	Pharmacokinetic
PKAS	Pharmacokinetics Analysis Set
PR	Partial Remission
PRES	Posterior Reversible Encephalopathy Syndrome
PT	Preferred Term
QTc	Corrected Q-T Interval
QTcF	QT interval corrected for heart rate using Fridericia's factor
RBC	Red Blood Cell
RED	Recommended Expansion Dose
RFS	Relapse Free Survival
RR	Interval between 2 consecutive r waves on an ECG
SAF	Safety Analysis Set
SAP	Statistical Analysis Plan
SAS	Statistical Analysis Software
SBP	Systolic Blood Pressure
SMQ	Standardised MedDRA Queries
SOC	System Organ Class
t _{1/2}	Apparent terminal elimination half-life
TLF	Tables, Listings and Figures
t _{max}	Time of the Maximum concentration
TTE-FAS	Time-to-Event Full Analysis Set

Abbreviations	Description of abbreviations
ULN	Upper Limit of Normal
V_z/F	Apparent Volume of Distribution During the Terminal Elimination Phase after Oral Dosing
WHO	World Health Organization
WHODD	WHO Drug Dictionary
WHODD(B2)	WHO Drug Dictionary (B-2 Format)
WHODD(B3)	WHO Drug Dictionary (B-3 Format)
WOCBP	Women of childbearing potential

List of Key Terms

Terms	Definition of terms
Baseline	Last available assessments of subjects as they enter a study before they receive any treatment.
Endpoint	Variable that pertains to the efficacy or safety evaluations of a study. Note: Not all endpoints are themselves assessments since certain endpoints might apply to populations or emerge from analysis of results. That is, endpoints might be facts about assessments (e.g., prolongation of survival).
Investigational period	Period of time where major interests of protocol objectives are observed, and where the test product or comparative drug (sometimes without randomization) is given to a subject and continues until the last assessment after completing administration of the test product or comparative drug.
Registration failure	A subject who signed the ICF and met the pre-registration criteria but did not meet all inclusion and exclusion criteria by day 8. These subjects received chemotherapy but never received ASP2215.
Screening	A process of active consideration of potential subjects for enrollment in a study.
Variable	Any quantity that varies; any attribute, phenomenon or event that can have different qualitative or quantitative values.

1 INTRODUCTION

This SAP contains a more technical and detailed elaboration of the principal features of the analysis described in the protocol and includes detailed procedures for executing the statistical analysis of the primary and secondary endpoints and other data.

The SAP is finalized and signed prior to database lock for primary analysis for the primary endpoint.

This statistical analysis is coordinated by the responsible biostatistician of Development API (Global Development, API). Any changes from the analyses planned in the SAP will be justified in the CSR.

2 FLOW CHART AND VISIT SCHEDULE

Details of the schedule of clinical assessments are available in the protocol.

3 STUDY OBJECTIVE(S) AND DESIGN

3.1 Study Objective(s)

3.1.1 Primary objectives

[Phase 1 part]

- To determine the maximum tolerated dose (MTD) and/or recommended expansion dose (RED) of ASP2215 concomitant with cytarabine/idarubicin as induction chemotherapy based on the status of the onset of dose-limiting toxicity (DLT).
- To evaluate the safety and tolerability of ASP2215 concomitant with cytarabine/idarubicin as induction chemotherapy and high-dose cytarabine as consolidation chemotherapy.
- To evaluate the safety and tolerability of ASP2215 in maintenance therapy after induction and consolidation therapy.

[Phase 2 part]

- To evaluate the efficacy of ASP2215 in combination with induction therapy in newly diagnosed FLT3 (FMS-like tyrosine kinase-3) -mutated AML (Acute Myeloid Leukemia) subjects.

3.1.2 Secondary objectives

[Phase 1 part]

- To characterize the pharmacokinetic (PK) parameters of ASP2215 concomitant with induction and consolidation chemotherapy.
- To evaluate the PK parameters of cytarabine concomitant with ASP2215.

[Phase 2 part]

- To characterize the PK parameters of ASP2215 concomitant with induction and consolidation chemotherapy.
- To evaluate the safety and efficacy of ASP2215 in combination with induction and consolidation therapy followed by maintenance therapy

3.1.3 Exploratory objectives

[Phase 1 part]

- To evaluate the efficacy of ASP2215 concomitant with induction and consolidation chemotherapy.
- To evaluate the pharmacodynamic (PD) parameters of ASP2215.

[Phase 2 part]

- To evaluate the additional efficacy measures for ASP2215 in combination with induction and consolidation therapy followed by maintenance therapy

3.2 Study Design

This study is a Phase 1/2, open-label, single-arm study in patients with newly diagnosed AML. The phase 1 part evaluates the dose of ASP2215 using the Bayesian-continual reassessment method (hereinafter, Bayesian-CRM) and the Phase 2 part evaluates the safety and the effect of ASP2215 in combination with induction and consolidation therapy followed by maintenance therapy in newly diagnosed FLT3-mutated AML patients. This study is composed of two-Phase 1 parts, which are the dose-evaluation part and the expansion part, and the Phase 2 part; the target population for each part is newly diagnosed AML patients and newly diagnosed AML patients with FLT3 mutation, respectively. Phase 1 part will be conducted in Japan and Phase 2 part will be conducted in Asia Pacific countries.

[Phase 1 part (dose-evaluation part and dose expansion part)]

The dose evaluation part and the expansion part are considered as the Phase 1 part. The primary objective of the Phase 1 part is to determine the MTD and/or recommended expansion dose (RED) of ASP2215 concomitant with chemotherapy drugs as induction therapy based on the status of the onset of dose-limiting toxicity (DLT). Dose-evaluation part will first evaluate the tolerated dose and the expansion part will confirm the safety of the dose identified in the dose-evaluation part. Subject enrollment and DLT assessment will be continued until the criterion for enrollment completion shown in the following table for Bayesian-CRM is met.

Table Phase 1 part Dose Evaluation flow chart

Dose Level	Cohort 1	Cohort 2	...
1 (120 mg)	3 subjects	3 subjects	...
-1 (80 mg)		3 subjects	...

The flow chart illustrates the progression of subjects from Cohort 1 to Cohort 2. For the 1 (120 mg) dose level, 3 subjects from Cohort 1 are shown in a solid box, with a dashed arrow pointing to a dashed box containing '3 subjects' in Cohort 2. For the -1 (80 mg) dose level, a dashed arrow points from the 3 subjects in Cohort 1 to a dashed box containing '3 subjects' in Cohort 2. Dashed arrows also point from the Cohort 2 boxes to ellipses, indicating further progression.

The starting dose of ASP2215 in the dose-evaluation part is 120 mg. According to the Table, at least 3 subjects will receive ASP2215 at the assigned dose (120 mg, or 80 mg as necessary) for the determination of MTD and/or RED. The DLT assessment period for the dose-evaluation part is until the end of induction therapy Cycle 1 and until the end of consolidation therapy Cycle 1 for the dose-expansion part. Subjects who meet any of the

following criteria will be considered unevaluable for DLT and will be replaced by another subject in the cohort.

- A subject that receives less than 80% of the assigned dose of ASP2215 during DLT assessment period specified in each part (e.g., subject in dose assessment part who misses ≥ 3 daily doses during DLT assessment period of dose evaluation part and interrupts the study for a reason other than a DLT)
- Unable to assess the safety adequately during DLT assessment period specified in each part such as due to the lack of required safety assessment(s)

The decision of whether or not to proceed to the next dose of ASP2215 will be made through discussion among the sponsor, principal investigators, and medical advisor with reference to the recommended dose level calculated using Bayesian-CRM, the safety data, etc., and after review by the sponsor's responsible person. The MTD is defined as the highest dose of ASP2215 at which the posterior mean of the DLT incidence during Cycle 1 of induction therapy is estimated to be closest to 33%.

[Phase 2 part]

After achieving the objectives of the Phase 1 part, the Phase 2 part can be initiated. Subjects will receive ASP2215 at the recommended dose established in the Phase 1 part. The primary objective of the Phase 2 part is to evaluate the efficacy of ASP2215 in combination with induction therapy in newly diagnosed FLT3-mutated AML subjects. The target population will be limited to newly diagnosed FLT3-mutated AML. The primary analysis for the primary endpoint of the CR rate will be conducted when all registered subjects complete the induction therapy period.

After treatment discontinuation, subjects will have a 30-day follow-up visit for safety, after which the subjects will enter the long-term follow-up period for collection of subsequent AML treatment, remission status, relapse and survival (cause and date of death). Duration of long-term follow-up is until 3 years after the last subject first treatment or completion of 30-day follow-up of the last subject, whichever is longer.

3.3 Randomization

Randomization is not performed in this study since this is an open-label, uncontrolled study.

4 SAMPLE SIZE

4.1.1 Target Sample Size

[Phase 1 part]

6 subjects

Dose-evaluation part: At least 3 subjects per cohort (which may be changed according to the status of the onset of DLT and the number of cohorts)

Expansion part: At least 3 subjects

[Phase 2 part]

Approximately 80 subjects

4.1.2 Justification of Sample Size

[Phase 1 part: Dose-evaluation part]

To assess MTD and RED of ASP2215 as induction therapy concomitant with cytarabine/idarubicin in newly diagnosed AML subjects, 3 DLT evaluable subjects per dose level for 1 dose level were assumed. The sample size may increase depending on the occurrence of toxicities.

[Phase 1 part: Expansion part]

The sample size was set to 3 subjects to further assess the safety and efficacy of ASP2215 at the dose tested in the expansion part.

[Phase 2 part]

A sample size of 70 subjects in Phase 2 part provides more than 80% power to detect a 15% increase in CR rate from 55% (historical benchmark based on the RATIFY study, Stone et al, 2017.) to 70% at one-sided significance level of 0.05. To account for several subjects dropping out from the study, 80 subjects will be enrolled.

5 ANALYSIS SETS

In accordance with ICH recommendations in guidelines E3 and E9, the following analysis sets will be used for the analyses.

5.1 Full Analysis Set (FAS)

[Phase 1 part]

Subjects who meet all of the following criteria will be included:

- Received at least 1 dose of study drug
- Assessed for at least 1 efficacy variable after study drug administration

[Phase 2 part]

Subjects who meet all of the following criteria will be included:

- Received at least 1 dose of study drug
- Had at least one post-baseline bone marrow assessment

For the statistical analysis of some Time-to-Event efficacy variables, TTE-FAS will be used. TTE-FAS is defined similarly as the FAS, however, the criterion for bone marrow assessment is removed.

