6 ANALYSIS VARIABLES

6.1 Efficacy Endpoints

6.1.1 Response Definition

Antitumor response will be assessed on the days of bone marrow sampling based on the bone marrow findings, and peripheral blast count, neutrophil count, and platelet count. Preferably, samples from both bone marrow aspiration and biopsy should be obtained, but if the bone marrow aspiration was determined to be sufficient, biopsy may be omitted.

Antitumor response is defined per modified Cheson criteria (2003) or modified ELN recommendations (2017) as outlined below [Döhner et al, 2017; Cheson et al, 2003].

[Phase 1 part]

The assessment will be performed by the investigator. The results of bone marrow findings and peripheral blast count will be entered into the eCRF.

[Phase 2 part]

Bone marrow aspiration and/or biopsy samples and hematology samples are evaluated both centrally and locally. If bone marrow samples were obtained for unscheduled visits, those samples along with hematology samples should be submitted for central assessment.

Definitions

Complete Remission (CR):

CR is defined as a morphologically leukemia-free state at the post-baseline visit, having a neutrophil count of $\geq 1,000/\text{mm}^3$ and platelet count of $\geq 100,000/\text{mm}^3$, bone marrow myeloblasts $< 5\%$. There must be no evidence of Auer rods and no evidence of extramedullary leukemia. The blast counts in peripheral blood must be $\leq 2\%$.

Complete Remission with Partial Hematologic Recovery (CRh):

CRh is defined as a condition at the post baseline visit, having bone marrow myeloblasts $< 5\%$, partial hematologic recovery neutrophil count $\geq 500/\text{mm}^3$ and platelet count $\geq 50,000/\text{mm}^3$, no evidence of extramedullary leukemia and cannot be classified as CR. The blast counts in peripheral blood must be $\leq 2\%$.

Complete Remission with Incomplete Platelet Recovery (CRp):

CRp is defined as a condition that meets all of the CR criteria at the post-baseline visit, except for the unrecovered platelet count ($< 100,000/\text{mm}^3$).

Complete Remission with Incomplete Hematological Recovery (CRi):

CRi is defined as a condition that meets all of the CR criteria at the post-baseline visit, except for the unrecovered neutrophil count ($< 1,000/\text{mm}^3$) whether or not having unrecovered platelet counts).

Partial Remission (PR):

At a post-baseline visit, PR is defined as a condition with regeneration of normal hematopoietic cells in the bone marrow.

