If bone marrow myeloblasts between 5% and 25% and a decrease from baseline of at least 50% in the marrow myeloblasts, no detectable (or trace of residual) blasts, and no evidence of extramedullary leukemia, the response is classified as PR.

Not Evaluable (NE)/No Response (NR):

In the situation where no bone marrow assessments are performed or myeloblast value is missing, blast value from peripheral blood is missing or $\leq 2\%$, and extramedullary leukemia is missing or not done, the response will be classified as NE. In any case response cannot be categorized as CR, CRp, CRi, PR or NE, it will be categorized as NR.

Relapse:

Relapse after CR, CRh, CRp or CRi is defined as a reappearance of leukemic blasts in the peripheral blood ($>2\%$) or $\geq 5\%$ myeloblasts in the bone marrow not attributable to any other cause or reappearance or new appearance of extramedullary leukemia.

Relapse after PR is similarly defined with reappearance of significant numbers of peripheral blasts and an increase in the percentage of myeloblasts in the bone marrow to $> 25\%$ or $>2\%$ blast in peripheral blood not attributable to any other cause or reappearance or new appearance of extramedullary leukemia.

Best Response:

Best response is defined as the best measured response to treatment for all visits (in the order of CR, CRp, CRi, PR, NR and NE) post-baseline. Subjects who achieve the best responses of CR, CRp, CRi, or PR will be classified as responders. Subjects who do not achieve at least PR will be classified as non-responders.

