6.1.2 Primary Efficacy Endpoint

[Phase 1 part]

Not applicable.

[Phase 2 part]

- CR rate after induction therapy period

Defined as the number of subjects who achieve the best response of CR divided by the number of subjects in the analysis population during induction therapy period. Subjects with unknown or missing response, or who provide no information on response will be treated as non-responders and will be included in the denominator when calculating rates.

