7.4 Analysis of Efficacy

[Phase 1 part]

The efficacy analysis will be performed on the FAS.

For response variables, best response after each treatment therapy period will be summarized. The number and percentage of subjects in each category will be presented together with two-sided exact 95% CIs based on binomial distribution. Swimmer's plot will be presented for response variables.

For time-to-event variables efficacy analysis will be summarized using descriptive statistics. The survival curve and the median will be estimated using the Kaplan-Meier method and will be reported along with the corresponding 95% CIs.

[Phase 2 part]

The efficacy analysis will be performed on the FAS and TTE-FAS. The interpretation of statistical results will be based on the FAS. The TTE-FAS will be used to analyze OS and EFS. Analysis of MRD and MR will be performed using MAS.

Primary efficacy variable

For primary efficacy variable, CR rate after induction therapy period, the two-sided 90% exact CI by Clopper-Pearson method will be calculated. The lower limit will be used to compare with the benchmark of CR rate of 55%. The number and percentage of subjects in each category and swimmer's plot will also be presented. As a supportive analysis, CR rate after induction therapy period reported by Day 60 and CR rate after induction therapy period not being dependent on RBC and platelet transfusion (No Transfusion of RBC and Platelet within 1 week prior to disease assessment) will also be calculated.

Other efficacy variables

For other efficacy variables, analysis method will be described as follows:

Categorical variables:

The number and percentage of subjects in each category will be presented together with two-sided exact 95% CIs based on binomial distribution. Swimmer's plot will be presented for response variables.

For response assessment variables, best response rate after each treatment therapy will be summarized. The number and percentage of subjects in each category will be presented together with two-sided exact 95% CIs based on binomial distribution. For subjects who undergo HSCT, any response assessment data after HSCT will not be used (i.e. for those subjects, only response assessment data before HSCT will be used).

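### The Phase 2 FAS drops dosed subjects with no post-baseline marrow from the primary CR rate, although the SAP classes them as non-responders; this can only raise the rate tested against 55%

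*SAP*

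**What the plan says.** **Analysis sets.** SAP section 5.1 (Phase 2 part) requires at least one dose of study drug for the FAS, and also that the subject "Had at least one post-baseline bone marrow assessment". The TTE-FAS is the same set without the marrow criterion. Its stated use is narrow: "For the statistical analysis of some Time-to-Event efficacy variables, TTE-FAS will be used".

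**Which set governs.** Section 7.4 (Phase 2 part) states: "The interpretation of statistical results will be based on the FAS". It then adds: "The TTE-FAS will be used to analyze OS and EFS". The primary CR rate therefore falls to the FAS. Its test compares the lower limit of a two-sided 90% Clopper-Pearson interval with 55%.

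**Missing response.** Section 6.1.2 covers subjects whose response is not known. It says of them, and of those without any response data, that subjects "who provide no information on response will be treated as non-responders and will be included in the denominator when calculating rates". Section 6.1.1 provides a category for a subject without a marrow ("In the situation where no bone marrow assessments are performed or myeloblast value is missing"): NE if the blood-blast and extramedullary conditions are also met, NR otherwise. Under best response it adds: "Subjects who do not achieve at least PR will be classified as non-responders".

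**CR itself.** "CR is defined as a morphologically leukemia-free state at the post-baseline visit", and marrow myeloblasts must be below 5%.

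**Subgroups.** Section 7.8 (Phase 2 part) runs the subgroup analyses of the primary endpoint, as well as those of OS, on the TTE-FAS.

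**The concern.** The response rules and the analysis set pull in opposite directions. Sections 6.1.1 and 6.1.2 take the conservative course: no information counts as failure. The FAS then removes the dosed subjects with the least information, those with no marrow at all (for example after early death or withdrawal), before that rule can reach them. The rule still works for subjects whose marrow is unclassifiable or was taken only after induction. So a subject with a little information counts as a failure, while a subject with none disappears.

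Each subject removed is a certain non-CR, and the test is against a fixed 55% in a single arm, so nothing cancels the effect.

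Sections 7.4 and 7.8 also give the same endpoint two denominators. With any exclusion, the age or sex subgroups would sum to more subjects than the primary analysis contains.

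**Working it through.** **Inputs.**
- Null rate 55%, alternative 70%, one-sided alpha 0.05, 70 subjects for power, 80 enrolled (section 4.1.2).
- Success: lower limit of the two-sided 90% Clopper-Pearson interval above 0.55 (section 7.4).
- k, the number of dosed subjects with no post-baseline marrow, is not in the SAP. It is assumed and varied. All 80 enrolled are assumed dosed.

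**1. The plan's own figure.** At n = 70 the smallest successful count is 46. P(Bin(70, 0.55) ≥ 46) = 0.0452 and P(Bin(70, 0.70) ≥ 46) = 0.820. The stated power of more than 80% is reproduced; the sample size statement is not at fault.

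**2. Direction.** With x CRs, the FAS gives x/(80 − k) and all dosed subjects give x/80. x is the same in both, because no excluded subject can be a CR. For k ≥ 1 and x ≥ 1 both the rate and the lower limit are higher on the FAS.

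**3. Same CR count, two denominators.**

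| CRs | FAS: rate, lower limit | All 80 dosed: rate, lower limit |
|---|---|---|
| 51 (k = 2) | 51/78 = 65.4%, 0.5555, pass | 63.8%, 0.5400, fail |
| 50 (k = 3) | 50/77 = 64.9%, 0.5502, pass | 62.5%, 0.5273, fail |
| 49 (k = 5) | 49/75 = 65.3%, 0.5528, pass | 61.3%, 0.5146, fail |

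The decision differs at 51 CRs for k = 2, at 50–51 for k = 3 or 4, and at 49–51 for k = 5. At k = 1 it cannot differ, because 52 CRs are needed at both n = 79 and n = 80.

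**4. False success if the true rate among all dosed is 55%.** With k fixed, the CR probability among those with a marrow is 0.55 × 80/(80 − k), and false success = P(Bin(80 − k, 0.55 × 80/(80 − k)) ≥ critical count).

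| k | n | Critical count | CR probability in FAS | False success |
|---|---|---|---|---|
| 0 | 80 | 52 | 0.550 | 4.5% |
| 1 | 79 | 52 | 0.557 | 4.4% |
| 2 | 78 | 51 | 0.564 | 6.8% |
| 3 | 77 | 50 | 0.571 | 10.2% |
| 4 | 76 | 50 | 0.579 | 10.0% |
| 5 | 75 | 49 | 0.587 | 14.5% |

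If k is instead random, Bin(80, q) with mean 1, 2, 4 or 5, false success is 5.2%, 6.8%, 10.8% or 13.2%.

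**5. The other reading of 55%.** If 55% is the rate among FAS subjects only, exact alpha is below 5% at every n from 70 to 80 (maximum 4.97%, at n = 77).

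**6. Operating characteristics on all dosed subjects.** With n = 80 the test needs 52 CRs (65.0%): alpha 4.5%, and power 86% if 70% is the rate among all dosed.

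**The case against.** **Set membership comes first.** Section 6.1.2 divides by the analysis population, so a literal reader applies the FAS and only then the missing-response rule. That is a possible reading, and it makes the conflict one of effect rather than of wording. It does not remove the bias, and the SAP gives no reason for treating no information more favourably than partial information.

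**k may be small.** Any post-baseline marrow at any time admits a subject. At k = 0 or a fixed k of 1 there is no inflation and no decision changes. This stands, but the SAP does not establish that k will be so small.

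**The benchmark's denominator is not shown.** If 55% describes marrow-assessed subjects, alpha holds. This also stands. The SAP does not say that the benchmark is so restricted.

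**The exclusions will be visible.** Section 7.2.1 reports them by reason, and adding up the TTE-FAS subgroups recovers the all-dosed rate. Disclosure does not change the stated test, however. The two supportive analyses in section 7.4 (CR by Day 60, CR without transfusion dependence) do not restore the excluded subjects.

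**Power may fall.** If 70% is the rate among assessed subjects only, the all-dosed test needs 52 CRs from 80 − k subjects. P(Bin(80 − k, 0.70) ≥ 52) is 78% at k = 2, 67% at k = 4 and 61% at k = 5. This is a fair caveat and should be stated with the change.

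**Conclusion.** The concern holds; the analysis set is wrong as written and must be fixed, because the criterion can decide the primary conclusion. Relative to all dosed subjects the direction of the bias is certain. Its size rests on three assumptions: 80 dosed, an unknown k, and 55% as the rate among all dosed. Under these, a fixed k takes the false-success probability above the nominal 5% only from k = 2 upward. The inconsistency between sections 7.4 and 7.8 needs correcting whatever k turns out to be.

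**What to change.** Make the TTE-FAS (all subjects with at least one dose of study drug) the primary set for the CR rate. Count subjects with no post-baseline marrow as non-responders, as sections 6.1.1 and 6.1.2 already provide, and report the marrow-required FAS as supportive.

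- **Section 5.1:** extend the use of the TTE-FAS beyond time-to-event variables.
- **Section 7.4:** rest interpretation of the primary endpoint on the TTE-FAS.
- **Section 7.8:** no edit; it then agrees.

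Section 4.1.2 needs no change if 70% is meant as the rate among all dosed; if it is meant among assessed subjects, power should be restated.

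The change needs no new data or patients. The reported CR rate may be slightly lower. If the protocol, which was not available for this review, defines the FAS in the same way, it must be aligned or the change justified in the CSR.
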